FULL TITLE OF THE CLINICAL STUDY

What is the clinical experience of maintaining patient safety in hospital in patients with temporary or permanent loss of cognitive function? A Mixed Methods Study

Protocol Final Version 1.0 06.11.2024
(Last updated 11.05.2026)

Short title: Clinical Experience of Maintaining Patient Safety in Hospital

Acronym: CEMPSIH

IRAS Project ID: 347285

Study Sponsor: University of Nottingham

Sponsor reference: **24065**

Funding Source: This study is part of a PhD study funded by a scholarship awarded by the Engineering and Physical Sciences Research Council (EPSRC).

STUDY PERSONNEL AND CONTACT DETAILS

Sponsor: Contact name	University of Nottingham [name] Head of Research Integrity, Governance & Compliance University of Nottingham [name] [contact]
Chief investigator:	Asst. [name] Associate [name] Human Factors Research Group Faculty of Engineering University of Nottingham Phone: Email: [contact]
Co-investigators:	
[name] [name] Principal Research Fellow, NIHR MindTech Research Centre Institute of Mental Health Email: [contact]
 
[name] Principle Research Fellow Centre for Rehabilitation and Ageing Research School of Medicine, Queens Medical Centre Email: [contact]
 
[name] Student ID: [name] Human Factors Research Group [contact] Email: [contact]

Study Coordinating Centre:	Human Factors Research Group Faculty of Engineering, University of Nottingham, [name]

SYNOPSIS

Title	What is the clinical experience of maintaining patient safety in hospital in patients with temporary or permanent loss of cognitive function? A Mixed Methods Study
Short title	Clinical Experience of Maintaining Patient Safety in Hospital (CEMPSIH)
Chief Investigator	Associate [name]
Objectives	To test whether there is a universal professional experience of maintaining patient safety in hospitals, with patients who have impaired cognitive function
Study Configuration	Mixed Methods, Multi-centre, Exploratory Sequential Strategy
Setting	Secondary care - Acute Hospital Trusts
Number of participants	128 participants overall. Up to 32 participants per Hospital (16 Nursing staff, 8 Therapists and 8 Medical Doctor or associates)
Eligibility criteria	Direct patient facing healthcare workforce responsible for managing and preventing accidental falls in the NHS.

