In the UK, 30 - 50% of accidental falls in hospital lead to some injury and 1-3% of those sustain a fracture (Morris and O'Riordan, 2017). In-patient falls are a significant cause of morbidity and mortality, with an estimated 247,000 occurring annually at a cost of £2.3 billion to the NHS (NHS improvement 2017; RCP 2020). In-patient falls have consistently been the biggest single category of reported incidents since the 1940's (Morgan et al., 1985). Little has changed in the 39 years since the Morgan et al. (1985) paper and with falls accounting for 85% of all hospital acquired conditions in the USA (Attenello et al., 2015) it is safe to say this is a global issue. A recent Australian study estimated that the annual cost of attempts to prevent in-hospital falls across six health services consumed AU\$590 million per year in resources. The areas of greatest investment were 18% physiotherapy, 14% 24 hour observation, 12% falls assessments and 11% falls prevention alarms (Mitchell et al., 2018) and there is a lack of quality research to support their efficacy as falls prevention strategies (National Institute for Health and Care Excellence, 2019).

The generalisable level of success of these strategies is still not known (Montero-Odasso et al., 2022). It seems that health services across the world are investing time and effort in strategies for which there is an absence of evidence (Mitchell et al., 2018). The recently published World Guidelines for Falls Prevention (Montero-Odasso et al 2022) has confirmed there remains no research supporting the use of technology such as falls alarms or nonslip socks (NSS) in hospitals and as such recommends only standard falls prevention methods. As a result of increasing reimbursement costs for hospital treatments, in 2008 the Centres for Medicaid & Medicare Services, health insurance companies in the United States of America (US), removed reimbursement to hospitals for costs incurred by patient falls and any associated trauma (Shorr et al., 2018) resulting in increasing financial burden to hospitals. The impact on staff suffering 'second victim phenomena' (Kappes et al., 2021) as a result of adverse incidents and the cost to patients who suffer pain, disability, and death is incalculable (Potter et al., 2016).

STUDY OBJECTIVES AND PURPOSE

PURPOSE

- To establish the barriers to preventing accidental falls in hospital and understand what interventions are perceived to work best to prevent falls.

PRIMARY OBJECTIVE

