- To disprove the null hypothesis that “there is no universal clinical experience of accidental fall prevention in hospitals with patients who have impaired cognitive function”.

SECONDARY OBJECTIVES

[figure not shown]
- To inductively generate a questionnaire to be distributed to healthcare professionals and care workers in a future study.
- To gather an evidence base for the co-created design and testing of fall prevention interventions as part of the longer term PhD project

The investigator has completed the HRA tools which have confirmed the study is classed as research and that it does not require NHS REC review. The investigator has also successfully undertaken the Good Clinical Practice training to provide public assurance that the rights, safety and wellbeing of research participants are protected and that research data are reliable.

STUDY DESIGN

STUDY CONFIGURATION

This is a multi-centre qualitative study utilising a purposive sampling strategy. Healthcare workers directly involved in preventing falls in hospital will be invited to contribute to the study via an email from their ward manager or clinical lead. Participants will be asked to respond directly to the researcher to indicate their interest in the study. They will be selected to ensure Medical and Surgical wards are represented to ensure generalisability of outcomes. Overall aim will be for up to 16 participants from the nursing team, registered and unregistered, up to 8 therapist participants and up to 8 doctors (*Figure 1- Participant Study Flowchart*).

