- Any healthcare professional or associated support staff involved in putting fall prevention measures in place in an acute ward environment
- Any healthcare professional or associated support staff involved in caring for patients and their relatives after an accidental fall in an acute ward environment
- Ability to give informed consent

Exclusion criteria

- Any healthcare worker with no medical or surgical ward experience
- Any healthcare worker under the age of 18 years old
- Any healthcare worker working exclusively in Critical Care or high dependency units or Paediatrics as countermeasures and levels of observation are different in these areas and have separate guidance and policies.

Expected duration of participant participation

Study participants will be participating in the study for a total of 4 hours over a period of 3 months.

Participant Withdrawal

Participants will withdraw from the study:-

- if consent is withdrawn
- if they become unwell
- If it is not safe for them to continue due to safety reasons outlined in the simulation risk assessment

Participants may be withdrawn from the study either at their own request or at the discretion of the Investigator. The participants will be made aware that this will not affect their employment rights. Participants will be made aware (via the information sheet and consent form) that should they withdraw the data collected to date cannot be erased and may still be used in the final analysis.

Informed consent

All participants will provide written informed consent. The Informed Consent Form will be signed and dated by the participant before they enter the trial. The Investigator will explain the details of the trial and provide an opportunity to go over any questions from the Participant Information Sheet that they received with the invite, ensuring that the participant has sufficient time to consider participating or not. The Investigator will answer any questions that the participant has concerning study participation.

Informed consent will be collected from each participant before they participate in any part of the study. One copy of this will be kept by the participant, one will be kept by the Investigator.

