The participant will be invited to play their usual professional role in a 30 minute scenario depicted by simulation and will be run 8 times over 2 separate days in each Trust using an actor. Using the safety of 'a simulation of a fall in an acute setting' rather than observations in practice the investigator will observe the participants behaviour and actions during the simulation of a patient having an accidental fall. Abdulmohdi and McVicar (2023) found there was a significant increase in deduction and analysis when using simulation compared to observations in practice. An additional advantage of a simulation is that the participants can be more confident in their discussion without the need to defend team culture compared to being observed in clinical practice. It is also easier to create the patient fall safely thereby maintaining the least powerful position for the investigator, as feedback in a hypothetical situation has not resulted in patient harm or reflected on their practice so the feeling of being judged is avoided (Humphries, 2003). There is also no compelling professionalism to require the investigator to prevent a participant causing harm to a patient or to draw attention to an omission heightening the potential power dynamic between researcher and participants (Humphries, 2003). The simulation will be held on the Trust premises to ensure ease of access for participants and minimise time away from clinical practice.

Following completion of the simulated scenario a 90 minute debrief focus group will reflect on the impact of the simulation and hear from the participants how this relates to their experience in practice. Michie et al. (2011) recommends a three-step process to investigate behaviour and this will be used as a framework for the focus group discussion alongside Critical Decision Making (CDM) (Weitzenfeld J.S, 1990). The investigator will use a semi structured design.

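### The primary hypothesis is limited to patients with impaired cognition, but nothing in the scenario, focus-group, coding or pooling text ties the themes to those patients

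*Combined protocol and SAP*

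**What the plan says.** The restriction to impaired cognition stands in three places. The full title concerns patient safety "in patients with temporary or permanent loss of cognitive function". The Synopsis objective is "To test whether there is a universal professional experience of maintaining patient safety in hospitals, with patients who have impaired cognitive function". The Primary Objective section sets out to disprove the statement that "there is no universal clinical experience of accidental fall prevention in hospitals with patients who have impaired cognitive function".

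The Purpose, just above the Primary Objective, has no such limit: "To establish the barriers to preventing accidental falls in hospital and understand what interventions are perceived to work best to prevent falls". The Synopsis describes eligible staff as "Direct patient facing healthcare workforce responsible for managing and preventing accidental falls in the NHS", and the inclusion criteria list falls-related roles, for example "Any healthcare professional or associated support staff involved in putting fall prevention measures in place in an acute ward environment".

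In Analyses – Methods, "the investigator will observe the participants behaviour and actions during the simulation of a patient having an accidental fall". Study Configuration describes the simulation in similar terms. The focus group then reflects on the simulation and asks how it relates to participants' own practice. Transcripts are coded openly to detect patterns. Step 18 of the Study Regimen brings together themes from all simulations and focus groups. Under Sample size and justification, sampling continues until repeated themes indicate whether experiences are homogeneous.

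**The concern.** A conclusion about staff experience with a defined group of patients needs data that can be traced to that group. Here the group is named in the hypothesis, but nothing in the described data collection or analysis identifies it. If themes are pooled without recording which patients were being discussed, a finding of shared experience may describe in-patient falls generally. The error could also run the other way: experience with the target patients might be homogeneous, but mixing in talk about other patients could make it look varied. In either case the primary hypothesis would be accepted or rejected on material that does not address it.

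**Working it through.** **Counts, for scale.** Participants: 4 per simulation (1 doctor, 1 therapist, 2 nursing team) × 4 simulations per day × 2 days × 4 sites = 128. Simulations: 4 × 2 × 4 = 32. Focus groups: 2 per day × 2 days × 4 sites = 16. These agree with the plan's maximum figures of 128 participants, 32 simulations and 16 datasets. No power calculation is given, and the point does not depend on one.

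**Tracing the restriction through the plan.** Apart from the title and the two statements of the objective, the only use of the word cognitive in the supplied text is in the name of cognitive load theory (Informed consent section). That concerns how staff perform, not patients.

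| Element | Where | Patients it refers to |
|---|---|---|
| Title, Synopsis objective, null hypothesis | Title page, Synopsis, Primary Objective | Impaired cognition |
| Purpose | Purpose | Falls in hospital generally |
| Ward choice | Recruitment | By patient age and fall-risk conditions |
| Scenario | Study Configuration; Methods | A patient who falls; cognition not stated |
| Procedure | Study Regimen, steps 1 to 18 | No step mentions patients' cognition |
| Focus group | Methods | Participants' own practice, no restriction |
| Coding | Methods | Open pattern detection, no label for patient type |
| Synthesis | Study Regimen, step 18 | All themes pooled |
| Stopping rule | Sample size and justification | Any repeated themes |

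**Does the unstated scenario detail decide the matter?** Take both possibilities.

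1. *The actor's patient is not cognitively impaired.* Then the shared stimulus is outside the target group, and target material arises only if participants raise it.
2. *The actor's patient is cognitively impaired in every run.* Then the simulation and the decision timeline built from it (step 13) do concern the target group. But the focus group goes on to practice in general, and the Informed consent section says the focus group, not the simulation, supplies the main body of work. Once coded without a label and pooled at step 18, an excerpt about a confused patient and one about any other patient are indistinguishable.

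Under both possibilities, a reader of the final themes cannot tell which of them bear on the hypothesis.

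**The stopping rule.** As an illustration, suppose the same barrier to preventing falls came up in all 16 groups, always in talk about patients in general. The rule on repeated themes would be met, yet no excerpt would concern impaired cognition. Nothing in the text prevents this.

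**The case against.** The strongest reply is that this is silence, not contradiction. The protocol nowhere says that the simulated patient is cognitively intact. A scenario written to serve the title could portray impairment without conflicting with any passage. The script and discussion guide are not among the supplied documents, and some figures are not shown. Because the focus group starts from the shared simulation, a suitable script would steer the discussion. All of this stands. It rules out the reading that the study is designed around cognitively intact patients or necessarily answers a different question. It does not remove the gap, because the discussion of wider practice, the coding, the pooling and the stopping rule would still be undifferentiated.

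A reader might infer four further things that the documents do not support:

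- *That temporary and permanent loss must be separated.* Both words appear in the title, where they read as inclusive scope. Neither statement of the objective asks for a comparison.
- *That the future questionnaire would have the wrong target.* The questionnaire objective is not limited to impaired cognition, and nor is the Purpose.
- *That eligibility needs a criterion on experience with such patients.* Sampling is purposive and the criteria select staff by role. The gap can be closed without changing who takes part.
- *That the reconsent wording redefines the population.* It discloses that falls, rather than patient safety at large, were the topic. Its contrast is with the umbrella term, not with a patient group.

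**Conclusion.** The point holds as a gap between the primary objective and the methods as written. The hypothesis is about patients with impaired cognition, while the text on scenario, discussion, coding and pooling gives no means of attributing themes to them, and the homogeneity judgement could be reached on general-falls material. The gap concerns the primary objective and all of up to 16 datasets. No numerical size can be given: the documents do not say how much of the discussion will concern the target patients, and participants may well raise them unprompted.

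The conclusion assumes that no separate coding frame or discussion guide already records this distinction. If one does, the protocol needs only to say so. The Purpose and the secondary objectives are not affected. This should be corrected, but it does not call the design as a whole into question.

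**What to change.** 1. In Study Configuration and Methods, state that the actor portrays a patient with impaired cognition in every run. The topic withheld from participants is falls, and the title already names cognitive loss, so this does not disclose it.
2. Add a focus-group prompt on patients with impaired cognition.
3. Tag each coded excerpt as related or not related to impaired cognition. Base the primary conclusion, and the homogeneity judgement for the primary objective, on the related excerpts. Report the rest as secondary.

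Alternatively, widen the title and primary objective to in-patient falls in general, which would match the Purpose.

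The cost is wording in the scenario and discussion guide, one code attribute and a little extra coding work. Some general-falls material becomes secondary. The planned 128 participants, 32 simulations and 16 focus groups are unchanged. If any sessions have already been held, the tagging can still be applied to their transcripts, and the protocol should record what the actor portrayed.

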This will provide up to 2 nurses, 1 therapist and 1 doctor in each simulation. This will provide 4 datasets for analysis at each hospital and this process will be repeated at up to 4 hospitals to deliver up to 16 datasets. Each group will participate in a 30 minute simulation which will simulate a patient having an accidental fall and will be recorded. Observation with notes by the investigator will inform discussion in the focus group to follow. The participant will be reconsented after the simulation as they will now be made aware that the focus is specifically on patient falls rather than all aspects of patient safety. If participants wish to withdraw they will be informed that, as per the initial consent form, their data to this point will be retained and used anonymously. In preparation for the focus group Critical Decision Method will be used to extract themes and codes to inductively generate a questionnaire for a future study. If the participant agrees to continue they will then join a larger group for the discussion around the simulation. This will be recorded for the investigators use only and the subsequent analysis will be fed back to the participants prior to publication and any further study to verify an accurate summary of the discussion. Patient and Public Involvement (PPI) representatives will be consulted on the evolving themes for their insights.

Participant numbers:-									
Hospital Site	Site 1		Site 2		Site 3		Site 4		Totals
Morning	Day 1	Day 2	Day 1	Day 2	Day 1	Day 2	Day 1	Day 2	
1 st Simulation 08.30-9.00	1 x Doctor 1 x Therapist 2 x Nursing Team	1 x Doctor 1 x Therapist 2 x Nursing Team	1 x Doctor 1 x Therapist 2 x Nursing Team	1 x Doctor 1 x Therapist 2 x Nursing Team	1 x Doctor 1 x Therapist 2 x Nursing Team	1 x Doctor 1 x Therapist 2 x Nursing Team	1 x Doctor 1 x Therapist 2 x Nursing Team	1 x Doctor 1 x Therapist 2 x Nursing Team	Up to 32 participants
2 nd Simulation 9.30-10.00	1 x Doctor 1 x Therapist 2 x Nursing Team	1 x Doctor 1 x Therapist 2 x Nursing Team	1 x Doctor 1 x Therapist 2 x Nursing Team	1 x Doctor 1 x Therapist 2 x Nursing Team	1 x Doctor 1 x Therapist 2 x Nursing Team	1 x Doctor 1 x Therapist 2 x Nursing Team	1 x Doctor 1 x Therapist 2 x Nursing Team	1 x Doctor 1 x Therapist 2 x Nursing Team	Up to 32 participants
Focus Group 10.00-12.00	8 Participants from the 2 morning Simulations discuss the simulation together								Up to 8 datasets
Afternoon									

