 17. Investigator will share themed analysis for comment. Method to suit participant such as Teams meeting, email, face to face or phone call.
 18. Investigator will bring together themes from all simulations and focus groups and synthesise any generalised views ensuring anonymity.

Compliance

Non-attendance of any staff member will be followed up with a phone call to number acquired during the consent process (their preferred form of communication). Participants will be offered the opportunity of an alternative date where available.

There is some contingency built into each simulation and focus group to allow for 2 participants not to turn up to their simulation. The focus group will be made up from 2 simulation groups and therefore should be a group of up to 8 for the discussion. Group numbers below 4 or with any profession not represented will not be considered quorate. In this event the investigator will attempt to organise an additional session for consented people who were unable to attend.

Criteria for terminating the study

In the unlikely event that the study is to be terminated on one or all sites the research data will be archived.

ANALYSES

Methods

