The focus group will be recorded, transcribed and analysed using Nvivo 14 (a software application to assist with coding) assigning meanings through essence capturing (Saldaña, 2021) by creating codes. These codes will be generated for the purpose of pattern detection to interpret data and deduct meaning (Vogt et al., 2012). This can be interpreted as imposing values or as reductionist but using constructivist principles will allow valuing multiple perspectives and will establish a deeper understanding of staff experience (Creswell, 2018). It is difficult to completely remove the investigator's values when analysis is done, but by sharing the analysis with the participants and the research team there is transparency and reflexivity, recognising the 'importance of self' (Humphries, 2003). The analyses will be discussed with the participants so any disagreement will also be recorded for the reader to consider. The primary intent of the qualitative phase is to design a measure that is grounded in issues raised by patient facing staff and PPI representatives rather than individual opinion or experience.

Sample size and justification

The investigator is seeking to involve a small number of relevant direct patient facing healthcare workers to provide in depth information about the lived experience of preventing and managing in-patient falls. By purposefully involving participants who are charged with preventing in-patient falls as part of their usual practice the investigator will be able to collect in depth knowledge of the experience and associated heuristics. 8 simulations and focus groups in 4 different hospitals on different geographical sites are planned generating 16 datasets. The investigator will continue until repeated themes suggests there is a degree of homogeneity in experiences or not (Creswell, 2018). This is with the intention of adopting a phenomenological approach but depending on the data arising sampling could continue to allow grounded theory to inform the questionnaire (Creswell, 2023). The final sample size will

not be determined until a sufficient database has been collected to develop the content of the questionnaire for a future study.

ADVERSE EVENTS

The occurrence of an adverse event as a result of participation within this study is not expected and no adverse event data will be collected.

ETHICAL AND REGULATORY ASPECTS

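### Up to 16 focus groups are themed together and judged by repeated themes, with no step separating repetition within one hospital from repetition across hospitals

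*Combined protocol and SAP*

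**What the plan says.** **Objective.** The primary objective is framed as disproving a null of no universal clinical experience of fall prevention in hospitals. The synopsis puts the same aim as a universal professional experience.

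**Structure.** Study Configuration says "This will provide 4 datasets for analysis at each hospital" and that "this process will be repeated at up to 4 hospitals to deliver up to 16 datasets". The Methods section says the simulation "will be run 8 times over 2 separate days in each Trust using an actor". The Compliance section says "The focus group will be made up from 2 simulation groups and therefore should be a group of up to 8 for the discussion". The participant table (Figure 2) places two simulations and one focus group in each morning and each afternoon, on two days per site.

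**Evidence base.** The sample size section states "8 simulations and focus groups in 4 different hospitals on different geographical sites are planned generating 16 datasets". Sampling continues until repetition of themes suggests that experiences are, or are not, to some degree homogeneous.

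**Synthesis.** The Study Duration text has all groups analysed and themed collectively. In the Study Regimen, step 16 themes the session, step 17 shares that analysis with participants, and step 18 will "bring together themes from all simulations and focus groups" and draw out generalised views.

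**Dependence.** The ethics section accepts that participants are likely to know each other or to have worked together.

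The text has no comparison between hospitals, no table of themes by hospital, and no rule on how many hospitals a theme must appear in.

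**The concern.** A claim about hospitals in general is replicated by hospitals. Four groups drawn from one hospital's staff, who are likely to be colleagues, are not four separate confirmations that an experience holds elsewhere. If they are counted or read as such, a feature of one site can look more widespread than it is.

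Two things are at stake. The first is the conclusion on the primary objective: repetition is the only stated basis for judging homogeneity, and the plan does not say at which level the repetition must occur. The second is the questionnaire for the later study, which is to be built from these themes and could carry one site's practice forward as if it were general.

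**Working it through.** **1. Reproduce the plan's count.** Inputs are from Study Configuration and Figure 2.

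- Focus groups: 4 hospitals × 2 days × 2 per day = 16.
- Simulations: 4 hospitals × 2 days × 4 per day = 32.
- Participants: 32 simulations × 4 people (2 nurses, 1 therapist, 1 doctor) = 128.

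The figures of 16 and 128 both reproduce. The sample size sentence could be read as 8 focus groups per hospital, but Figure 2 shows 8 simulations and 4 focus groups per hospital, which is the reading that gives 16.

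**2. How far a confined theme can recur.** With 4 groups per hospital:

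- theme in one hospital only: at most 4 of 16 groups (25%);
- theme in two hospitals only: at most 8 of 16 groups (50%), with no support from the other two.

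**3. The repetition rule.** It sets no number of groups and no number of hospitals. Four groups at the first hospital are enough for a theme to repeat, so as written the rule could be met before a second hospital is visited.

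**4. What 16 nested groups are worth.** Design effect = 1 + (m − 1) × ICC with m = 4 groups per hospital; effective number = 16 / design effect. The documents give no intra-hospital correlation (ICC), so the values below are assumptions.

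| Assumed ICC | Design effect | Effective number of groups |
|---|---|---|
| 0 | 1.0 | 16.0 |
| 0.1 | 1.3 | 12.3 |
| 0.3 | 1.9 | 8.4 |
| 0.5 | 2.5 | 6.4 |
| 1 | 4.0 | 4.0 |

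**5. Do the existing safeguards separate the two levels?**

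- Representing medical and surgical wards addresses ward type, not hospital.
- Different geographical sites make a comparison possible, but none is planned.
- Participant checking, in the Study Regimen order, takes place at step 17, before the cross-group synthesis at step 18.
- Consultation with patient and public representatives is not a between-site check.

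**The case against.** **This is a qualitative study.** Sampling is purposive and coding is constructivist. Nothing says themes will be counted out of 16 or that 16 is an independent sample size, and the phase is meant to inform a questionnaire. This stands as a limit on the numbers: there is no planned estimate to which a design effect or confidence bound attaches. It does not remove the point, because the protocol itself sets a universality hypothesis and a repetition rule, and the level of repetition matters to both.

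**The plan already shows the structure.** Study Configuration and Figure 2 are laid out by site, step 16 themes each session before synthesis, the rule allows a finding of no homogeneity, and disagreement is recorded. So a theme could be traced to its hospital. True, but no step requires this or makes the conclusion depend on it.

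**The degree of dependence is unknown.** The documents say only that participants are likely to know or have worked with one another. They do not describe local policies, training or equipment, and the background cites national guidance that applies across hospitals. This stands, and is why a range is shown.

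**A stronger reading is tempting.** A reader might infer that a theme from one or two hospitals will probably pass as universal, and support it as follows. If a theme is wholly hospital-determined and present in half of hospitals, it appears in at least 12 of 16 groups with probability 31% (25% for three hospitals plus 6.25% for four), against 3.8% if groups were independent. The documents do not support that inference:

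- The plan has no 12-of-16 threshold.
- Twelve of 16 under this assumption means three or four hospitals, never one or two.
- The 31% needs an ICC of 1. Under a beta-binomial model with prevalence 0.5, the probability is 6.2%, 10.5% and 14.2% at ICC 0.1, 0.3 and 0.5.

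The same applies to the contrast in one-sided 95% lower bounds for a theme seen everywhere: 0.05^(1/4) = 47% by hospital against 0.05^(1/16) = 83% by group. It compares only ICC 1 with ICC 0, and it assumes random sampling, which the study does not use.

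**Conclusion.** The concern holds as an unguarded risk in how themes are combined, not as a demonstrated error. The nesting, the collective theming and the absence of a hospital-level rule are all in the text. What follows without further assumption is that a theme confined to one or two hospitals can recur in up to 4 or 8 of 16 groups, and that repetition could be declared within one hospital. The loss in effective number of groups, from 16 to between 12.3 and 4, rests on assumed correlations from 0.1 to 1 and equal numbers of groups per hospital.

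A reader might also infer that more groups are needed. The documents do not support this: the sample size is not derived from any precision target, and the remedy needs no extra participants. The change is worth making because it alters what can be concluded about universality.

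**What to change.** Amend step 18 of the Study Regimen and the sample size section:

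- Tag each transcript with its hospital and theme within hospital before combining.
- Report a theme-by-hospital matrix: the number of participating hospitals in which the theme was found, then the number of groups within each.
- Base the judgement that themes are repeated, and any statement of a universal or shared experience, on recurrence across participating hospitals and not on the pooled count of groups.
- Report themes found in only some hospitals with that count. Do not label them local automatically, since silence in a semi-structured discussion is not absence of the experience.
- Describe the evidence base as up to 4 hospitals with 4 focus groups in each. Use the number of hospitals that actually take part as the denominator, because with only one or two sites a requirement to appear in every hospital is met too easily to support universality.

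The cost is one NVivo attribute, one table and a few sentences. The downside is a less favourable statement of the evidence base: up to four hospitals instead of 16 datasets.
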